Brain metastases affect one third of all adult cancer patients¹. Stereotactic radiosurgery (SRS), a highly precise modality for focal ablative radiotherapy, is standard of care for patients with limited brain metastases¹⁻². However, many patients will experience decline in neurocognitive function after brain SRS^{3,4,5,6}, given the potential for high doses to eloquent brain tissue. Neurocognition has emerged as a critical endpoint along with survival and tumor control in brain tumor clinical trials^{7,5,8}. Radiation-induced cognitive impairment after SRS can manifest as a range of cognitive problems, particularly deficiencies in memory, language, attention and executive functioning, depending on tumor location and dose delivered to critical brain tissue.

Any focal intervention in the brain should occur with a detailed understanding of the brain's functional and anatomic relationships relative to the target⁹⁻¹⁰. With the aid of modern magnetic resonance imaging (MRI) techniques, eloquent brain regions can be well demarcated in imaging studies and projected into three-dimensional (3D) space. In particular, diffusion tensor imaging (DTI) tractography with automated white matter segmentation can be used to identify critical white-matter pathways (tracts) of the brain^{11,12,13}. 3-D volumetric MRI and automated brain parcellation software can be used to segment discrete areas of the brain including the hippocampus, a structure critical for memory^{14,15}. In radiation planning, particularly in brain SRS planning, these new technologies have **not yet** been prospectively tested for sparing healthy and sensitive parts of the brain from high doses of radiation.

These novel imaging techniques also allow us to directly and non-invasively measure microstructural changes after radiotherapy to critical brain structures *in vivo*. Using diffusion imaging biomarkers, we have shown that radiation therapy results in dose dependent damage to uninvolved white matter¹⁶ with greater susceptibility to injury among white matter tracts critical for neurocognition¹⁷. Our studies with 3-D volumetric MRI and automated parcellation of the hippocampus have shown dose-dependent hippocampal atrophy after fractionated brain radiotherapy^{15,18}. These imaging biomarkers hold promise to help elucidate the mechanisms behind radiation-induced cognitive decline.

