With RCI at 3-months post-SRS as the outcome variable, linear regression modeling will be used to analyze patient-specific (e.g. age, sex), tumor-specific (e.g. histology, number of lesions, imaging progression), and treatment-specific (e.g. previous chemotherapy, anti-epileptic drugs) predictors of neurocognitive change after cognitive-sparing SRS. Model selection will be based on Akaike Information Criterion (AIC)^{88,89}. Given the small sample size and multiple variables of interest, this will be an exploratory analysis. Given that cognitive-sparing on this study will not be performed at the sacrifice of tumor coverage, we expect the overall local control and survival rates in the cohort to be comparable to those in other studies of SRS alone for patients with 1-3 brain metastases^{1,5,6,22}. Treated tumor local control rates will be assessed at 3- and 6-months post-SRS. Local tumor control of each treated lesion will be assessed with modified RANO criteria⁸⁴ where tumor progression is defined as >25% increase in the size of a treated lesion. Tumor progression of treated metastases will be evaluated independently of the development of new lesions⁵. Local tumor control rate at 6 months and overall survival rate (death from any cause) at 12 months will be compared to historical values⁵ using a 1-sample t-test.

Secondary Objective Analyses

The imaging biomarker of each structure (mean white matter diffusivity metrics and hippocampal volume) will be modeled as a function of time using linear mixed effect models^{13,16}. These models are well-suited for longitudinal analysis since they account for within-subject correlation between repeated measures, and allow for incomplete outcome data. Individual structures will be classified based on whether they received greater or less than the median dose for that structure across all patients. The interaction of dose and time will be tested within the model to assess whether dose mediates longitudinal trends. In addition, potential fixed-effect covariates will be selected from a list of patient and tumor-specific variables, such as age, sex, tumor size and location. Model selection will be based on AIC. To account for correlated observations within subjects, patient-specific random intercepts and time-associated slopes will be tested.

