Associations between average changes in imaging biomarkers at the 3-month time point and RCI of domain-specific neurocognitive tests will be estimated using linear models with model selection based on AIC. As an exploratory analysis, associations between early changes in imaging biomarkers, measured at the 1-month time point, with RCIs of domain-specific neurocognitive tests will also be estimated using the same methodology. This may help to identify those metrics that can serve as early indications of 3-month neurocognitive deterioration.

TractCrawler imaging software will be used to generate slices perpendicular to the medial axis for each white matter structure. We will then generate slice-averaged values of diffusion imaging metrics as a function of length along the medial axis of the tract, defined in a common coordinate system across patients at each time point. Sensitivity metrics will be generated per-patient and per-slice to quantify the degree to which changes in diffusion metrics in that slice differ from the mean change across the entire structure for each of the post-RT time points compared to baseline. T-tests can then be used to identify regions (slices or groups of slices) along the length of the white matter tract where changes are significantly greater or smaller than the rest of the tract.

Feasibility: Accrual of 60 patients over 3 years is feasible given that over 100 brain metastases patients are treated yearly at our institution that would meet eligibility criteria. Patients will be compensated \$100 for study participation to offset transportation costs and time. We will enroll approximately 3-4 patients per month, allowing full enrollment to be completed by around 15-20 months. This will allow all testing and analyses to be completed within the four-year grant period. The imaging methods, processing techniques and automated KBP capabilities are already integrated into our brain tumor imaging and brain SRS workflow, making the study execution highly feasible. The team of investigators and collaborators have already established a successful research and clinical collaboration for this and other research projects and grants.

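### The along-tract analysis uses no slice dose, so its sensitivity metric cannot separate local dose from local sensitivity

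*Protocol*

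**What the plan says.** The last paragraph on tract imaging under Statistical Considerations, Secondary Objective Analyses, cuts each tract into slices perpendicular to its long axis. It then fixes three things.

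- The metric: "Sensitivity metrics will be generated per-patient and per-slice to quantify the degree to which changes in diffusion metrics in that slice differ"
- The comparator: "from the mean change across the entire structure for each of the post-RT time points compared to baseline"
- The test: "T-tests can then be used to identify regions (slices or groups of slices) along the length of the white matter tract"

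Dose appears earlier in the same section, in the mixed models of structure-level biomarkers ("mean white matter diffusivity metrics and hippocampal volume"). There it is a split per whole structure: "Individual structures will be classified based on whether they received greater or less than the median dose for that structure across all patients". That split carries the dose-by-time term: "The interaction of dose and time will be tested within the model to assess whether dose mediates longitudinal trends". No slice dose is computed, adjusted for or stratified on anywhere.

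The Protocol's opening section reports from the investigators' earlier work that "radiation therapy results in dose dependent damage to uninvolved white matter". Background and Significance describes radiosurgery as confined to the metastases. The paragraph on knowledge-based planning says targets will differ in location between patients.

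**The concern.** If damage depends on dose, and dose varies along a tract, a slice can depart from the tract mean for two reasons: it is more sensitive per unit dose, or it received more dose. The metric contains both and has no term to separate them, yet it is named as a measure of sensitivity.

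The structure-level dose split does not help. It compares patients with one another on a single dose value per tract, whereas the problem is a gradient within the tract. The one analysis that could localise an effect leaves dose out, and the one that includes dose averages over the whole tract.

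At stake is the interpretation of a secondary imaging result. The Protocol chose several of its avoidance tracts partly for their radiation sensitivity (Critical Structures for Sparing), so a map carrying that label could be read as bearing on the trial's own rationale. Correcting for the number of slices tested would not remove the bias.

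**Working it through.** The Protocol gives no slice count, sample size, alpha or power for this analysis, so there is no figure to reproduce. Except for n = 48 (Sample Size Determination) and α/β = 2.5 Gy (Radiation Planning Dose Constraints), all inputs below are assumptions.

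**1. What the t-test estimates.** Let slice j have sensitivity s_j and average dose effect g_j across patients. The expected deviation is s_j·g_j minus the average of s_k·g_k over the tract. With equal sensitivity s everywhere this becomes s·(g_j − mean g). It is zero at every slice only if the average dose effect is the same along the whole tract.

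**2. Hand calculation.** Assume 20 slices, 7 of them (about one third) at r times the dose elsewhere, mean dose scaled to 1, equal sensitivity, an effect of 0.2 noise SD at mean dose, and independent slice noise with SD 1.

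- Dose elsewhere = 1/(0.35r + 0.65); segment dose = r times that.
- Shift = 0.2 × (segment dose − 1).
- SE = √(1/7 − 1/20)/√48 = 0.305/6.93 = 0.0440.
- Chance of p < 0.05 ≈ P(Z > 1.96 − shift/SE) for r > 1.

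| r | Segment dose | Shift | Shift/SE | By hand | Simulated |
|---|---|---|---|---|---|
| 1 | 1.000 | 0 | 0 | 5% | 6% |
| 1.5 | 1.277 | 0.055 | 1.26 | 24% | 23% |
| 2 | 1.481 | 0.096 | 2.19 | 59% | 53% |
| 3 | 1.765 | 0.153 | 3.48 | 94% | 88% |

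The simulation uses the same set-up but lets dose vary between patients and slices, which adds noise and lowers the rates a little. No slice is truly more sensitive in any row, so every flag is false.

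**3. Dependence on where dose falls.** A second simulation used 20 slices, a bell-shaped dose profile (peak 12 Gy, SD 3 slices), a change of 0.1 × sensitivity × dose plus unit noise, a test at 0.05/20 = 0.0025 per slice, and 1,000 runs.

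| Scenario, n = 48 | No dose term | Slice dose in model |
|---|---|---|
| Equal sensitivity, peaks spread evenly: highest slice flag rate | 3% | 1% |
| Equal sensitivity, peaks clustered: highest slice flag rate | 50% | about 0% |
| Mid-tract twice as sensitive, peaks spread evenly: mid-slice flag rate | 26% | 25% |
| Mid-tract twice as sensitive, peaks clustered elsewhere: average flag rate over all slices | 27.5% | 4.5% |

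With n = 30 the clustered, equal-sensitivity rate is 25% without dose and about 0% with it.

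**4. Form of the dose term.** The models in step 3 were fitted to data generated as linear in dose. The Protocol converts dose with the linear-quadratic formula, so a third check used equal sensitivity, a response proportional to D(1 + D/2.5), an assumed mean dose of 4 Gy and r from 1.5 to 3. The segment was falsely flagged in 73–99% of runs by the unadjusted t-test, in 51–98% by a linear dose-by-position term, and in about 11–13% when biologically effective dose was used. The last figure is still above 5%, so the standard errors also need checking.

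**The case against.** The strongest defence is that the paragraph's aim is descriptive. It seeks "regions (slices or groups of slices) along the length of the white matter tract where changes are significantly greater or smaller" than in the rest of the tract, and a t-test on the deviation answers that. The term sensitivity is defined in the same paragraph as a deviation from the tract mean. This stands: the test is valid for locating change, and the fault lies in what the label invites.

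A reader might go further and infer that the analysis maps dose rather than sensitivity. The documents do not support that. The group result reflects average dose effect multiplied by sensitivity. Bias needs dose to cluster at the same position across patients, and the Protocol gives no such distribution. With evenly spread dose, a truly sensitive segment is found about as often without dose (26%) as with it (25%). A reader might also infer that segments will be reported as radiosensitive and used to set future limits; no section says so.

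The gradient is partly bounded. Exclusion criterion 4 removes tumours invading a spared structure, and Table 3 caps each tract at 12 Gy for single-fraction treatment. Neither makes dose even below the cap, and the Protocol lets the standard clinical plan be used where sparing is not achievable.

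Finally, slice covariates might sit in an analysis plan that is not shown. But the Protocol already states metric, comparator and test, all without dose, so this is a design choice rather than an omitted detail.

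**Conclusion.** The point holds in limited form. As written, the along-tract analysis cannot separate local dose from local sensitivity, and the structure-level dose split cannot repair that. The premises are the Protocol's own: focal dose and dose-dependent white-matter damage.

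The size is unknown in advance. On assumed inputs the false-flag rate runs from small (at most 3% per slice with evenly spread dose) to large (about 23%, 53% and 88% for a segment at dose ratios 1.5, 2 and 3, single test at 0.05). These figures rest on assumed slice counts, dose profiles, effect size and noise, and they illustrate direction rather than predict this trial. Dose adjustment helps, but a linear dose term should not be the default.

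This concerns a secondary imaging analysis only. The primary endpoint, the sample size and patient management are unaffected.

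**What to change.** Amend the along-tract paragraph as follows.

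- Resample the treatment-plan dose onto the slices already generated, and show each tract's mean slice-dose profile beside its change map.
- Keep the t-tests as a description of where change occurred, and rename the metric, for example to slice deviation from tract-mean change.
- Base any statement about regional sensitivity on a per-tract model of slice change with slice dose, slice position and patient random effects. Enter dose flexibly (for example as a spline) or as biologically effective dose with α/β = 2.5 Gy, the value the Protocol already uses. Because some lesions are treated in three fractions, compute the latter from dose per fraction.
- Report whether the regional finding survives a change of dose form, and check the standard errors at patient level, for example by resampling patients.

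The cost is some extra processing and a conclusion that depends on the assumed dose-response form. No new scans are needed: the Protocol already co-registers images across time points and registers the planning MRI to CT. If the dose work is not done, the minimum is to drop the word sensitivity and state that the map does not account for dose.

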RSI-modeling of DWI: As a summary, the diffusion-weighted signal in each voxel is modeled as a linear combination of the response functions of different diffusion components with pre-specified diffusion properties (primary and secondary apparent diffusion components) and geometries (spherical or cylindrical). The contribution of each component to the overall signal is then estimated using a Tikhonov-regularized linear regression. The signal contribution from any one or combination of these components can then be isolated and used for further analysis. In brain tumors, the RSI framework consists of four components: spherically-restricted, cylindrically-restricted, cylindrically-hindered and spherically-free. The signal contribution of the cylindrically restricted component can be thought to arise from pools of water whose motion is impeded (trapped) by the white matter axons, and can then therefore be used in its segmentation while minimizing the influences of other populations of water (such as edema) within the same voxel.

Estimation of tensor and RSI-derived biomarkers: Diffusion data acquired using b-values of 0, 500, and 1500 s/mm² will be fit to a single tensor using a linear least-squares optimization of the log-transformed signal at each voxel. The diffusion tensors will then be used to estimate 3D volumes of the mean, axial, and radial diffusivity as well as the FA. Second, the entire diffusion data set will be fit using the RSI framework described previously to generate signal contributions of the 4 diffusion components (spherically restricted, cylindrically-restricted,

cylindrically-hindered, and spherically free). The fraction of the total signal described by the cylindrically-restricted component will be estimated at each voxel location, and used as an RSI-derived feature of white matter structure.

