SRS Planning with Knowledge-based Planning (KBP): Radiation treatment plans are manually planned by medical dosimetrists and physicists using commercial treatment planning software. Brain SRS planning is especially complicated given the higher doses, small margins, and critical structures involved. This planning process is time-consuming and inefficient, requiring multiple iterations over several days, with a wide variation in plan quality^{66,67}. Automated knowledge-based SRS planning, which was developed by [name] and his team, is an innovative approach which eliminates the variability and inefficiency of standard planning, allows the addition of new critical structures and optimization objectives into complex treatment plans, and delivers high quality, deliverable brain SRS plans^{68,69}. This automated SRS planning system is ideal for use in this trial where new clinical objectives for critical structures (eloquent white matter tracts, hippocampus) will need to be optimized and accounted for in planning each brain SRS case, with targets in different areas around the brain. This system is already integrated into our clinical workflow with a fast planning turn-around time of 20-35 minutes.

Table 1: White Matter and Hippocampal Structures for Cognitive-Sparing

Eloquent Cognitive Structures
Cingulum
Uncinate Fasciculus
Inferior longitudinal fasciculus
Corpus Callosum
Arcuate fasciculus
Inferior frontostriatal tracts
Fornix
Hippocampus

*all bilateral except Corpus Callosum

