Patients will be seen by the treating physician on the day of SRS, and on subsequent follow-up visits. They will be followed closely with clinical and imaging exams for safety and tumor recurrence (i.e., 1 month, 3 months, 6 months post-SRS). All treatment-related toxic effects and adverse events will be recorded according to NCI Common Terminology Criteria for Adverse Events, version 4.0. Local tumor control rates for each treated lesion will be assessed according to the revised Response Assessment in Neuro-oncology (RANO) criteria^{81,82}.

Payment

Parking for study patients related to study visits will be complementary. Subjects will be compensated \$100 for participation in this study to help compensate for time and travel costs.

Statistical Considerations

Primary Objective Analysis:

Cognitive test results (pre- and post-SRS) will be scored based on standardized published norms^{72,87}. Cognitive deterioration will be defined as a decline of greater than 1 SD on at least 1 of the 7 cognitive tests (Table 2, not including BDI or FACT-BR). Fisher's exact 2-group binomial test will be used to compare the proportion of patients with 3-month post-SRS cognitive deterioration between the current cognitive-sparing SRS study and previously reported with standard SRS.⁵ Further analyses of pre- to post-SRS cognitive change for each test will

utilize a reliable change index (RCI)⁸⁷. This index is derived from the standard error of measurement of each test, and it represents the 90% confidence interval (CI) for the difference in raw scores from baseline to follow-up that is expected if no real change has occurred. RCI values below the 90% CI are indicative of significant decline. RCIs also account for practice effects, which is ideal for this study where evaluations are 3 months apart. One-sample t-tests ($H_0=0$) will be used to determine significant group decline in RCIs by test and cognitive domain. Pearson correlation coefficients will be used to assess associations between RCIs and depression scores. Bonferroni corrections will be applied to control for Type I errors due to multiple comparisons.

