Sample Size Determination: This study is powered based on the endpoint of cognitive deterioration at 3 months post-SRS, defined as decline of greater than 1 standard deviation (SD) from baseline on at least 1 of the neurocognitive tests. This was the primary endpoint of the Alliance N0574 study. With 60 accrued patients

and assuming a 20% drop-out rate, we will have sample size $n=48$. We have 85% power to detect a change in the cognitive deterioration rate from 64% in standard SRS to 42.5% in the current cognitive-sparing study with $n=48$ (Fisher's exact 2-group binomial test, 2-tailed $\alpha=0.05$).

4. Risks

The anticipated risk to patients in this study is minimal.

The MRI scans to be obtained at baseline would be added on to the same scan performed for routine SRS planning for patients. Follow up MRI would be standard of care imaging and would be obtained regardless of whether the patient is on or off study. These scans do not involve any radiation exposure. There are no additional risks associated with the research scans aside from discomfort due to the additional 8-10 minutes of scan time required. However, these scans are frequently performed as part of standard of care during presurgical planning without adverse effects. Some patients may experience claustrophobia in the MR scanner and may require the use of medications for this, as is prescribed routinely for brain MRIs when indicated.

Intracranial SRS would be performed identically to standard of care, except for adding additional regional avoidance for cognitive sparing. In cases where sparing of these structures cannot be performed without sacrificing treatment of the tumor or another critical structure, this will be recorded and the default will be the standard clinical plan. While clinical benchmarks of SRS quality will not be sacrificed on this study, there is a possibility that changing the SRS plan to achieve cognitive sparing may change the dose distribution to other structures in the brain. It is unclear whether this would change any clinical outcomes since SRS plans must adhere to the same rigorous standards as the current standard of care.

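### Slice-by-slice t-tests along each tract are planned without multiplicity control, a rule for slice groups or an exploratory label, so the chance of a false region per tract analysis is well above 5%

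*Protocol*

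**What the plan says.** The last analysis under Secondary Objective Analyses (Section 3, Statistical Considerations) concerns location within a tract. "TractCrawler imaging software will be used to generate slices perpendicular to the medial axis for each white matter structure". For each patient and slice, a sensitivity metric measures how far "changes in diffusion metrics in that slice differ from the mean change across the entire structure", and this is done "for each of the post-RT time points compared to baseline". Then "T-tests can then be used to identify regions (slices or groups of slices) along the length of the white matter tract" whose change is significantly larger or smaller than in the rest of the tract.

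Three other places set the scale:

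- **Tracts.** Table 1 lists seven white matter structures plus the hippocampus, with the footnote "all bilateral except Corpus Callosum".
- **Metrics.** The paragraph on tensor and RSI-derived biomarkers uses the tensors to "estimate 3D volumes of the mean, axial, and radial diffusivity as well as the FA", and adds the cylindrically restricted signal fraction as a further white matter feature.
- **Multiplicity.** The one statement in the document is "Bonferroni corrections will be applied to control for Type I errors due to multiple comparisons". It closes the cognitive paragraph under Primary Objective Analysis, directly after the t-tests on reliable change indices and their correlations with depression scores.

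**The concern.** The protocol does not merely leave this analysis open. It names a test, a unit of testing and the claim to be made from it. Followed as written, it runs a t-test at every slice, and possibly at groups of slices, and reports the significant ones as regions. With many slices per tract, the chance that at least one is significant when nothing differs is no longer 5%.

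The analysis also lacks the label that would excuse this. The protocol uses the word exploratory where it means it: for the regression models of cognitive change, and for the 1-month biomarker associations described just before the slice analysis. The slice maps have no such label, and the opening section lists longitudinal white matter damage within primary objective 2.

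At stake is the reading of the result. A map of tract segments that change more than their surroundings invites the conclusion that those segments are more radiosensitive. A reader given such a map, with the word significantly attached, would assume an error rate that the method does not deliver.

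**Working it through.** The protocol states no figure for this analysis, so there is nothing to reproduce. The check asks what false-region rate the stated method gives.

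**Inputs from the protocol**

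- Tracts, counting sides: 6 bilateral × 2 + corpus callosum = 13.
- Time points after treatment: 3 (1, 3 and 6 months).
- Metrics: 4 from the tensor (mean, axial and radial diffusivity, FA), or 5 with the RSI fraction.
- Patients: 60 less 20% = 48. This is the drop-out assumption for the cognitive endpoint, borrowed here.

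**Inputs assumed, because the protocol gives none**

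- Slices per tract: 10 to 100.
- Correlation between slices: from none to very smooth.
- Alpha: 0.05 two-sided, borrowed from Sample Size Determination.
- Form of test: one-sample t-test of slice change minus the patient's own tract mean.

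**Step 1. Independent tests.** The chance of at least one false positive in m tests is 1 − 0.95^m. This gives 0.302 for m = 7, 0.401 for 10, 0.642 for 20 and 0.923 for 50.

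**Step 2. Correlated slices, first-order autoregressive.** Null simulation with 48 patients, each slice centred on the patient's tract mean, and correlation 0.8 between neighbours. At least one false slice appeared in 31% of tract analyses with 10 slices, 45% with 20 and 68% with 40. Over correlations from 0.5 to 0.95 and the same slice counts, the range was 28% to 82%.

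**Step 3. Correlated slices, Gaussian smoothness.** Same design, 1,500 runs per setting, smoothness given as full width at half maximum (FWHM) in slices:

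| Slices | FWHM 0 | 3 | 5 | 10 | 20 |
|---|---|---|---|---|---|
| 20 | 0.63 | 0.40 | 0.33 | 0.19 | not run |
| 30 | 0.80 | 0.55 | 0.42 | 0.27 | 0.17 |
| 50 | 0.93 | 0.74 | 0.61 | 0.38 | 0.25 |
| 100 | 0.99 | 0.93 | 0.82 | 0.61 | 0.37 |

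The settings tried run from about 0.17 to 0.99. The lowest is more than three times the nominal 0.05.

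**Step 4. Searching over contiguous slice groups.** This adds little when slices are smooth (30 slices, FWHM 5: 0.42 rises to 0.46) and more when they are independent (20 slices: 0.63 rises to 0.83).

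**Step 5. Bonferroni over the slices of one tract.** The rate falls to about 0.01 to 0.06 under Gaussian smoothness, and to 3% to 6% in the autoregressive model. It is therefore valid, and conservative when slices are smooth.

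**Step 6. Sign-flip test with the maximum statistic over slices.** The rate was about 4% to 7% (300 runs per setting), consistent with 5% within simulation error.

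**Step 7. Number of tract analyses.** 13 × 3 × 4 = 156 and 13 × 3 × 5 = 195, if every tract, time point and metric is mapped. At the lowest simulated rate and the smaller count, 156 × 0.17 ≈ 27 analyses would be expected to show a false slice if no regional difference existed anywhere, against 156 × 0.05 ≈ 8 at the nominal rate.

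**The case against.** The best defence is that this is detail for an SAP, which may exist but is not at hand. The sentence is permissive (tests can be used), it sits among the secondary analyses, and the main imaging analyses are mixed models on whole structures. Primary objective 2 concerns longitudinal trends and their correlation with cognition, not location within a tract. All of this stands, and it limits the weight of the point. It does not remove it. The protocol states a test and a significance claim whose error rate is wrong as written, and it does not call the analysis exploratory.

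A second defence is that the Bonferroni sentence is worded generally and may be meant for the whole study. Its position ties it to the cognitive tests, and its family of tests is not defined. If it were extended, it would work for single slices. A reader might infer that it is the wrong tool because neighbouring slices are correlated. That is not so: Bonferroni holds under any dependence and loses only some power. It would not cover groups picked after seeing the data, because the number of tests is then unknown.

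A reader might also infer that groups will be picked because they look extreme. The protocol does not say so; they could be fixed segments in the common coordinate system. What stands is that nothing fixes them in advance.

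**Conclusion.** The point holds as a gap in error control for one supporting imaging analysis. The slice tests have no multiplicity rule, no advance definition of slice groups and no exploratory label, and the Bonferroni sentence is not extended to them.

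The size is an illustration. With 48 patients, alpha 0.05 and correlation 0.8, the chance of at least one false slice per tract analysis is about 30% with 10 slices and about 70% with 40. Over wider assumptions it is about 17% to 99%. A single figure such as 3 to 7 in 10 cannot be derived from the protocol, because slice count, correlation and alpha are all missing.

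A reader might go further and conclude that most reported segments would be noise. That does not follow. These are chances of any false slice when no true difference exists. The share of reported segments that are false depends on how many true differences there are, which nothing in the protocol settles. The supported statement is that false regions are to be expected in many tract analyses if the text is followed literally. The primary cognitive endpoint and the sample size are not touched.

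**What to change.** - Replace the plain t-test with a sign-flip permutation test per tract: flip the sign of each patient's whole profile of slice differences, and refer the result to the distribution of the maximum statistic, or maximum cluster size, over the tract. To cover data-driven groups, use cluster size, or take the maximum over every slice and group that may be reported.
- If Bonferroni is preferred, say that it applies here, state the number of slices, and fix any slice groups in advance.
- Name one lead metric and one lead time point, and apply Holm or FDR across the 13 tracts.
- Label all other maps exploratory and drop the word significantly from their description.

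The cost is a few sentences in the protocol or SAP and a short script. Fewer segments will be called significant, and Bonferroni would give up some further power when slices are smooth. No change to data collection or sample size is needed.
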